5. MODEL OF CARE – THE ISPU INTERVENTION

The ISPU is an innovative care model that builds on the JC-certified CSC/PSC design by increasing coordination of care using a patient/caregiver-centric design. C3FIT's ISPU two coordinated units, *Stroke Central* and *Stroke Mobile*, are connected by a technology-enabled coordinating bridge, *Stroke Connect* that addresses the entire care continuum for the patient, from acute through hospital care to 1-year post-discharge care. Stroke Central and Stroke Mobile can be thought of as components of Stroke Connect; see Figure 5.

- **Stroke Connect** is comprised of Stroke Central and Stroke Mobile personnel and technology working in synergy to provide coordination and integration of care delivery and communication across the 1-year episode of care (see Figure 4). Stroke Mobile can access Stroke Central's specialist input through this key care coordination system.
- **Stroke Central** is the acute and in-hospital-based component of the ISPU. Responsible for the patient during EMS routing, ED care, and management while in-hospital, Stroke Central is comprised of a licensed health professional Coordinator and many key

Figure 5. Stroke Nodes and Systems of Care: CSC/PSC versus C3FIT's ISPU

[figure not shown]
specialist care delivery professionals. The Acute Stroke Team resides in Stroke Central and includes key personnel and functions of a CSC/PSC (that currently reside in the hospital setting) but in the IPU model also extends coordination of their care delivery into the Subacute and Chronic Nodes for management of care.

- The Acute Stroke Team expands into post-discharge recovery through Stroke Mobile, a care delivery team comprised of a licensed health professional and lay health educator who work directly with the patient and caregiver/family. During monthly visits in their home or care facility, Stroke Mobile's Care Team follows patients through their final phases of in-hospital stay and remains engaged during any post-hospital care at a rehabilitation unit or extended care facility and/or in their home. Stroke Mobile can access Stroke Central's specialist input virtually at any time through C3FIT's key care coordination system, Stroke Connect.

Technological facilitators will be utilized as part of the Stroke Connect coordination and integration mechanism, including:

- A data management and data collection portal, Vivify Health, which will be used by Stroke Central and Stroke Mobile to facilitate chronic disease management post-stroke, to monitor risk factor control, and to facilitate new symptom and/or complication recognition.
- Telemedicine audio-video capability to allow Stroke Central providers the capability to assist the Stroke Mobile team in evaluation and management in the home/facility, which facilitates real time communication and collaboration and allows virtual evaluation of the patient/caregiver for a higher level of care as required.
- An educational portal called dialogEDU provides a common educational platform for professional (RN, physician, EMS, pharmacist, etc.) and patient and caregiver education around stroke symptoms, complications, recovery and risk factor management, and lifestyle changes.

Figure 4. C3FIT Patient Flow Diagram – ISPU Arm Only

The ISPU intervention is designed to coordinate and integrate patient-centric, multidisciplinary, team-based initiatives that engage patients and caregivers/family members in care and recovery from arrival at the ED through 1-year post-stroke at home or facility. Initiatives in Stroke Central include: (1) daily (M-F) multidisciplinary rounds in the hospital (including physicians, residents, physical, speech, and occupational therapists, pharmacists, nursing unit representatives, and Advanced Practice Nurses); (2) use of a daily (“airline-type”) checklist administered by Stroke Central to evaluate guideline compliance; (3) use of proactive real-time care evaluation with a feedback loop for immediate correction of care deficiencies targeting complications; and (4) a central coordinating mechanism (Stroke Central) to enhance collaboration between professionals across the nodes of care.

Initiatives in Stroke Mobile include: (1) enrolling all stroke subtypes (ischemic (small and large vessel, embolic, and other), intracerebral hemorrhage, and subarachnoid hemorrhage); (2) utilizing a home/facility-based care delivery model that reduces the need for clinic visits; (3) invoking a home/facility-based model that focuses on caregiver/family (in addition to patients) to increase patient/caregiver/family engagement; (4) utilizing a lower cost care delivery team that broadly involves multiple layers of care (i.e. vascular neurology, internal medicine, rehabilitation physicians/therapists, nursing, advanced practice nursing, and lay educators); (5) tackling multiple risk factors in the management paradigm post-stroke; and (6) Involving a comprehensive care model that reflects the longitudinal care needs of the stroke patient for 1-year post-stroke.

Ensuring both implementation and fidelity is essential to ensuring our results can be attributed to the intervention. To this end, specific monitoring will be undertaken by the CCC and the Steering Committee to ensure intervention components are conducted as intended, including recording and assessment of training attendance, completion, and knowledge attained; monitoring of meeting frequency and attendance; and determining home visit procedure/visit compliance, completion, drop-out rates, and other strategies. We will closely monitor these and other components at the site level and intervene with their personnel if not performing.

6. BASELINE AND FOLLOW-UP ASSESSMENTS AND LABORATORY EVALUATIONS

The following outlines the Data Paradigms for Stroke Mobile based on obtained values for various scales and data points utilized. The guidelines establishing blood pressure and cholesterol goals are from the American Heart and Stroke Association.⁸

A. On-Study/On-Intervention Evaluations

The schedule of evaluations occurring after randomization while the subject is on-study and on (or about to start) intervention along with allowable time window in which evaluations may take place (± 30 days with a target of ± 14 days) is shown in Tables 7 and 8. Primary and secondary outcomes are considered a mandatory part of the protocol; remaining measures will be collected if patient/caregiver are able and/or available.

Table 7. Data Collection Paradigm: ISPU Arm, Stroke Central and Stroke Mobile

Item/Metric	In Hospital Prior to Discharge	Post Discharge Visit											
		Day 0-14	Month of Visit to Home/Facility										
		1	2	3	4	5	6	7	8	9	10	11	12
Informed Consent Confirmed	X	X	X	X	X	X	X	X	X	X	X	X	X
Demographics (Age, Gender, Race/Ethnicity, Marital Status, Zip Code of Residence, Income, and Education)*	X			X			X						X
Caregiver/Family identified*	X			X			X						X
Medical Record Number (MR #)*	X												
Get-With-The-Guidelines (GWTG) in-hospital data*	X												
Patient Medical History	X			X			X						X
Complications* ¹	X			X			X						X
National Institutes of Health Stroke Scale (NIHSS)*	X	X	X	X	X	X	X	X	X	X	X	X	X
Stroke Subtype*	X												
Prior stroke/Transient Ischemic Attack (TIA)*	X												
Risk factor profile* ²	X												X
Cholesterol panel or LDL*	X			X			X						X
Hemoglobin A1C (HBA1C)*	X			X			X						X
Perceived Support				SRU			SRU						SRU
Stroke Impact Scale (SIS)				SRU			SRU						SRU
Simplified Modified Rankin Scale (smRS)	X			SRU			SRU						SRU
Blood Pressure (BP) Control: at target	X	X	X	X	X	X	X	X	X	X	X	X	X
Lipid Control: LDL, at target	X			X			X						X
Diabetes Control: HBA1C, at target	X			X			X						X
Smoking Status	X	X	X	X	X	X	X	X	X	X	X	X	X
Body Mass Index (BMI)	X	X	X	X	X	X	X	X	X	X	X	X	X
Diet Assessment	X	X	X	X	X	X	X	X	X	X	X	X	X
Exercise Assessment	X	X	X	X	X	X	X	X	X	X	X	X	X
Mortality surveillance		X	X	X	X	X	X	X	X	X	X	X	X
Recurrence surveillance		X	X	X	X	X	X	X	X	X	X	X	X
Readmission surveillance		X	X	X	X	X	X	X	X	X	X	X	X
Time at Home		X		SRU			SRU						SRU
Depression History	X												
Depression: Patient Health Questionnaire (PHQ-9)		X	X	X	X	X	X	X	X	X	X	X	X
Caregiver Strain Index (CSI)		X		X			X			X			X

RED=Primary and Secondary Outcomes, BLACK=Additional Assessments by Stroke Mobile

SRU=UAB's Survey Research Unit

¹Complications monitored: Urinary tract infection, pneumonia, aspiration, deep vein thrombosis, skin breakdown, fall, myocardial infarction, depression, fever/other infection, and Afib.

²Risk factor profile: hypertension, diabetes, hyperlipidemia, smoking status, BMI, CHADS2VASC score, CRP, Afib, family history.

*Will be collected if patient/caregiver are able and/or available.

Table 8. Data Monitoring Paradigm: ISPU Arm, Stroke Mobile Visits 1-12

Item/Metric	In Hospital Prior to Discharge	Post Discharge Visit to Home/Facility											
		Day 0-14	Month of Visit										
			1	2	3	4	5	6	7	8	9	10	11
Glasgow Coma Scale (GCS)*	X												
Barthel Index*	X	X					X						X
Stroke education*	X	X	X	X	X	X	X	X	X	X	X	X	X
PT/OT/ST visits scheduled*	X												
Patient Medical History	X												
4-item Medication Adherence Scale*		X					X			X			X
Hill-Bone Compliance*		X					X						X
Epworth Sleepiness Scale*		X					X						X
Montreal Cognitive Assessment (MoCA)*		X					X						X
Frenchay Activities Index*		X					X						X
Antiplatelet use assessed, if appropriate*		X	X	X	X	X	X	X	X	X	X	X	X
Anticoagulant use assessed, if appropriate*		X	X	X	X	X	X	X	X	X	X	X	X
INR at-target, if appropriate*		X	X	X	X	X	X	X	X	X	X	X	X
Antihypertensive assessed, on intervention*		X	X	X	X	X	X	X	X	X	X	X	X
Antihypertensive assessed, at target*		X	X	X	X	X	X	X	X	X	X	X	X
Statin assessed, on intervention*		X	X	X	X	X	X	X	X	X	X	X	X
Hyperglycemia assessed, on intervention*		X	X	X	X	X	X	X	X	X	X	X	X
Hyperglycemia assessed, at target*		X		X			X						X
Smoking Cessation: On intervention, At target*		X	X	X	X	X	X	X	X	X	X	X	X
BMI: Discussed, at target*		X	X	X	X	X	X	X	X	X	X	X	X
Diet: Discussed, at target*		X	X	X	X	X	X	X	X	X	X	X	X
Exercise: Discussed, At target*		X	X	X	X	X	X	X	X	X	X	X	X
DVT assessed*		X	X	X	X	X	X	X	X	X	X	X	X
Skin assessed*		X	X	X	X	X	X	X	X	X	X	X	X
Mobility assessment* ¹		X					X						X
Depression intervention, if needed*		X	X	X	X	X	X	X	X	X	X	X	X
Caregiver Intervention, if needed*		X	X	X	X	X	X	X	X	X	X	X	X
Document tele- or phone consult to Stroke Central*		X	X	X	X	X	X	X	X	X	X	X	X
Stroke Mobile Team Conference attendance (monthly)*		X	X	X	X	X	X	X	X	X	X	X	X
Stroke Central Check-in with Stroke Mobile (daily)*		X	X	X	X	X	X	X	X	X	X	X	X
Establish plans for post intervention follow-up*													X
Self-reported Assessment of Life’s Simple Seven*		X											X
SRU=UAB’s Survey Research Unit													
¹Mobility Assessment includes: Berg Balance Test, Functional Reach Test, Timed Up and Go.													
*Will be collected if patient/caregiver are able and/or available.													

Intervention Discontinuation Evaluations. If the patient or caregiver/family declines follow up in-person visits, we will offer follow-up phone or virtual evaluations for primary and secondary outcomes and other assessments. If consent not provided for this, no follow up will occur.

Special Instructions and Definitions of Evaluations. Evaluations to be performed include: SIS and smRS, NIHSS, GCS, 4-item Medication Adherence, medication side effects, Hill Bone Compliance, Frenchay, MoCA, Barthel's Index, Epworth Sleepiness Scale, PHQ-9 depression scale, Caregiver Strain Index, blood pressure, Cholesterol panel, Hemoglobin A1c, INR (as appropriate), BMI, Smoking cessation, exercise assessment, diet assessment, readmission, recurrence, bleeding assessment and INR assessment (see Tables 7 and 8).

Final On-Study Evaluations. On study evaluations will be completed by Stroke Mobile and the University of Alabama Birmingham (UAB) SDCC Survey Research Unit (SRU) to include SIS and smRS and other assessments (see Table 5).

Concomitant Interventions. None.

Study Intervention Modifications. None.

Assessments. Tables 7 and 8 identify and define the assessments and the timeframe for each measurement parameter.

Other Laboratory Studies. None.

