(7) Exercise	Question(s) to assess patient adherence to recommendations of the AHA.	X	X ⁺	X ⁺	X ⁺
Mortality*	Will be assessed at visits. If needed, medical records will be collected from site, and the Adjudication Committee will review.		X	X	X
Recurrent Stroke*			X	X	X
Rehospitalization*			X	X	X
Time at Home	Assesses Time at Home (patient or caregiver home) versus at institution (for hospitalization, IPR, and/or SNF).		X ⁺	X ⁺	X ⁺
Depression (Patient)	Patient Health Questionnaire (PHQ-9)		X	X	X
Caregiver Strain	Caregiver Strain Index		X	X	X
*Results of these measures will be reported back to patient's treatment team for information/action. *SRU only. H: Collected at the Hospital prior to discharge by site personnel IPR: In-patient rehabilitation facility SNF: Skilled Nursing Facility					

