Recruitment and Informed Consent. The acute in-hospital study sample will include patients admitted to the hospital with suspected stroke symptoms. Potential participants (both patient and caregiver if available) will be approached for recruitment ideally within 5 business days post discharge ideally (to a maximum of 14 total days) for the participant. In the event that the patient is unable to provide consent, their surrogate can be consented. Patients will be identified by study personnel from ED and stroke service admission logs; pilot data suggests nearly complete case ascertainment. To assure that acute in-hospital recruitment and informed consent procedures are followed consistently across Sites, a guidance document will be prepared in consultation with Site PI's and other patient, caregiver and organizational stakeholders, and Site personnel will be trained consistently by CCC staff.

The post-hospital discharge study sample will include patients and caregivers who have a discharge diagnosis of stroke and who reside in each clinical site's defined geographic area. Potential participants will be approached prior to hospital discharge regarding their interest in participating in the study, and every effort will be made to consent both patient and caregiver at that time.

Patients and caregivers at an ISPU Site who participate in Stroke Mobile will receive 12 in-home visits from Stroke Mobile. At each visit, Stroke Mobile will conduct a physical assessment and administer specific clinical scales to determine functional status, medication adherence, fall risk, daily activity level, depression, and caregiver strain, among others. A phlebotomy (draw blood) will occur (cholesterol and HbA1c) according to the study time schedule.

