5. MODEL OF CARE – THE CSC/PSC ARM

Post-discharge, management and treatment of patients in the CSC/PSC arm will follow general clinical practice guidelines as is usually provided by the site in the management of all patients following a stroke, e.g. one-month clinic follow-up by a vascular neurologist. Patients will return to the CSC/PSC site per protocol for data collection research visits at 3, 6, and 12 months, and the University of Alabama Birmingham (UAB) SDCC Survey Research Unit (SRU) will contact them by phone at these times (see Figure 4). No C3FIT intervention management will be provided at these visits, however, usual standard of stroke care will occur. If there are emergent needs, the patient will be referred to that site's emergency department, patient's family physician, or the physician PI at the site.

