### **3.2. Modified Rankin Score (mRS)**

The mRS is a 7-point scale, ranging from 0 (normal) to 6 (dead), where at baseline the scores were from 0 to 5 (discharged dead were excluded from the study). During follow-up, patients were scored a 6 at the 3, 6 and 12-month follow-up if the patient died before the respective follow-up (even if the patient missed intervening visits). The mRS will be dichotomized as “good outcomes” of 0 to 2 points, and “poor outcomes” of 3 to 6 points. Analysis will use a mixed model approach (implemented through GLIMMIX) with the treatment-specific proportion of “good outcomes” modeled at months 0, 3, 6, and 12 (reported with the p-value for treatment differences at each time point). The primary outcome will be treatment differences in the change in the proportion with good outcomes between months 0 and 12, but differences to months 3 and 6 will also be estimated. These differences will be estimated with the same 4-level incremental adjustments, and with both unadjusted and inverse-probability weighted adjustment. Effect modification will be assessed by age, sex, race/ethnicity, stroke sub-type, stroke severity (discharge NIHSS dichotomized at 0 to 1 versus 2+), and nSES. With the discharge mRS as an outcome, the analysis will not be adjusted for baseline mRS.

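### All follow-up ends once a patient declines visits and calls, although Table 1 names site records as a source for deaths, recurrent strokes and readmissions

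*Protocol*

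**What the plan says.** Section 6.A of both arm protocols, under Intervention Discontinuation Evaluations, has the same rule. A patient or family declining in-person visits is first offered a substitute: "we will offer follow-up phone or virtual evaluations for primary and secondary outcomes and other assessments". The next sentence ends the matter: "If consent not provided for this, no follow up will occur". The same section says "Primary and secondary outcomes are considered a mandatory part of the protocol".

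Table 1 (section 1.B, both protocols) gives the source for mortality, recurrent stroke and rehospitalization: "Will be assessed at visits. If needed, medical records will be collected from site, and the Adjudication Committee will review". Section 8.C lists revocation of consent as a reason for discontinuation. Section 6.A does not say how that differs from declining contact, or whether records may still be used after contact is declined.

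On the analysis side, SAP 3.2 says that "patients were scored a 6 at the 3, 6 and 12-month follow-up if the patient died before the respective follow-up", including when visits in between were missed. Protocol section 9 gives patients who die a floor score and on that basis expects little further missing data. SAP 4.1 models time from discharge to death, recurrent stroke or rehospitalization without stating a censoring rule. SAP 4.2 ends follow-up at last follow-up, death or withdrawal, but only for time at home.

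Contact differs by design. ISPU patients "will receive 12 in-home visits from Stroke Mobile" (ISPU protocol, section 10.A). CSC/PSC patients return for "data collection research visits at 3, 6, and 12 months" (CSC/PSC protocol, section 5). Blinded telephone calls are made in both arms.

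**The concern.** The rule makes refusal of contact the end of all data collection, including for outcomes that may not need contact. Death, recurrent stroke and readmission can leave a trace in the enrolling site's records, and the plan already expects to use those records in some cases.

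Two things are at stake. First, mRS 6 and the floor score can be assigned only if the death is known. For a patient who has declined everything, a later death becomes a missing primary outcome instead of the worst one. The inverse-probability weights in SAP 3.1 use site, age, race/ethnicity, sex, NIHSS and neighborhood SES, so they cannot reflect deterioration after discharge. Second, the event outcomes lose events. SAP 4.1 allows that deaths and recurrent strokes may be few, and in that case admits covariates only while there are at least 10 events per factor. Lost events can therefore cost adjustment as well as precision. SAP 4.1 describes no weighting for these outcomes.

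**Working it through.** The documents state no refusal rate, loss rate or expected event count, so there is no figure to reproduce. The finding rests on the text. The arithmetic below only shows what the size depends on.

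**Inputs.** Sample size 1,262 (protocol summary), so n = 1,262 / 2 = 631 per arm if the split is equal (assumption). Event rate p = 12.7%, the background stroke readmission figure in Table 3 of the ISPU protocol, used for illustration only. Share declining all contact, d: assumed. Share of decliners' events falling after refusal, f: assumed 0.5 or 1.

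**Events lost per arm** = n × p × d × f. Expected events: 631 × 0.127 = 80.1.
- f = 0.5: 80.1 × 0.05 × 0.5 = 2.0, and 80.1 × 0.15 × 0.5 = 6.0
- f = 1: 80.1 × 0.05 = 4.0, and 80.1 × 0.15 = 12.0

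**Deaths missing from the 12-month mRS.** With 12-month mortality assumed at 3 to 10% and f = 0.5:
- low: 631 × 0.03 × 0.05 × 0.5 = 0.5
- high: 631 × 0.10 × 0.15 × 0.5 = 4.7, which is 4.7 / 631 = 0.7% of the arm

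**Effect on the comparison.** Because SAP 4.1 gives no censoring rule, two treatments of decliners are possible. The true arms are taken as equal in the first.

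1. Decliners counted as event-free to 12 months. Observed ratio, ISPU to CSC/PSC = (1 − d_I f) / (1 − d_C f), with f = 0.5:
   - 5% v 5%: 1.00
   - ISPU 15% v CSC/PSC 5%: 0.925 / 0.975 = 0.95
   - ISPU 5% v CSC/PSC 15%: 0.975 / 0.925 = 1.05

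2. Decliners censored at refusal, on average at mid-year, with hazard afterwards h times that of other patients. For uncommon events, true over observed hazard ratio = [1 + 0.5 d_I (h − 1)] / [1 + 0.5 d_C (h − 1)]:

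| Decline, ISPU v CSC/PSC | h | True / observed |
|---|---|---|
| 20% v 10% | 1 | 1.000 |
| 15% v 10% | 3 | 1.15 / 1.10 = 1.045 |
| 20% v 10% | 3 | 1.20 / 1.10 = 1.091 |
| 10% v 20% | 3 | 1.10 / 1.20 = 0.917 |
| 20% v 10% | 0.5 | 0.95 / 0.975 = 0.974 |
| equal d and h | any | 1.000 |

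A value above 1 means the observed ratio flatters ISPU; below 1, CSC/PSC. The sign changes when the arms are swapped or when later risk is lower. The distortion vanishes if declining is unrelated to risk, or if declining and later risk are the same in both arms. The loss of events and of mRS 6 scores remains in every row.

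**The case against.** A reader might infer that more is lost in the ISPU arm, because it has 12 visits against three, and that the trial therefore flatters ISPU. The documents do not support this. The rule is identical in both protocols, and refusing home visits does not trigger it: the patient must also refuse phone or virtual evaluation. ISPU visits come to the patient, deliver care and carry 9 × 20 = 180 dollars of additional reimbursement. CSC/PSC patients must travel to the site, receive no study intervention there, and are reimbursed only where the site elects to do so. Refusal could be higher in either arm.

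The possible distortion is also modest. With 3 to 10% mortality among 1,262 patients there would be 38 to 126 deaths, and the standard error of the log hazard ratio, √(4 / deaths), is about 0.32 to 0.18 before clustering. The largest value above, log 1.091 = 0.087, is 0.3 to 0.5 of a standard error. The protocol itself expects little missing data beyond deaths and morbidity.

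Table 1 presents records as a supplement to visits and does not state that they may be used without contact. The consent form may already separate refusing contact from refusing record use; it is not among the documents reviewed, so its silence cannot be charged to the plan. The SAP rule for mRS 6 does not depend on how a death is learned, and the DSMB monitors premature withdrawal.

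All of this stands, and it removes any claim about direction. It leaves the main point untouched: the protocol sentence says follow-up stops, and no section reviewed provides for looking at records afterwards.

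**Conclusion.** The point holds as a cheap improvement to a stated rule. As written, the rule discards later deaths, recurrent strokes and readmissions among patients who refuse all contact. It also turns their deaths into missing mRS values, although the plan already names a source that could supply some of these events.

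Under the assumptions shown, the loss is about 2 to 6 events per arm at a 12.7% event rate, or up to 12 if all the decliners' events are lost. About 0.5 to 5 deaths per arm would be missing from the mRS. These figures rest on assumed refusal of 5 to 15%, an equal split and assumed mortality. The documents establish neither a direction of bias nor a bias in the hazard ratio; both depend on refusal by arm and on later risk, which are not given.

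**What to change.** In section 6.A of both protocols, replace the sentence along these lines: if visits and phone or virtual evaluation are both declined, contact stops; unless the patient also withdraws permission to use records, and where consent covers it, vital status, recurrent stroke and readmission continue to be taken from site records to 12 months, with stroke-related hospitalizations adjudicated as for other patients. Record which type of withdrawal occurred, and report it by arm with dates.

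In SAP 4.1, state that event outcomes are censored at the end of record follow-up. In SAP 3.2, state that deaths found through records are scored 6.

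The cost is one sentence in each protocol, matching consent wording if it is not already there, one data field and two SAP statements. There are three limits. Site records miss events treated elsewhere. Patients already enrolled can be included only where their consent allows; the SAP introduction says 21 sites provided data, so this may be many of them, although the censoring rule and reporting by arm need no new consent. Surviving decliners remain missing on the mRS, so after refusal this group contributes only deaths. The SAP's rule for deaths after missed visits already has that property, and the report by arm should make it visible.
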